1.0 BACKGROUND AND RATIONALE

1.1 Soft Tissue Sarcomas

Soft-tissue sarcomas make up approximately 1% of adult malignancies and encompass approximately 70 different histologic subtypes¹. Most of these tumors are genetically complex and are highly unlikely to share a common mutation or alteration in signaling that would allow for treatment with an inhibitor to one molecule across all subtypes. Surgery is usually the first line of treatment in localized disease, while radiation or chemotherapy can be used in local disease that is unresectable due to size or location. Cytotoxic chemotherapy remains the standard of care for advanced and metastatic disease. Doxorubicin is the most active single agent with a response rate of approximately 20-25%². In some instances, patients may not be a candidate for either one of these therapies based on age or other comorbidities leaving no viable treatment options. Prognosis is dismal in the metastatic setting with a median survival of less than 12 months even with therapy.

1.2 Pazopanib

Pazopanib is a multitargeted tyrosine kinase inhibitor that has been shown to have efficacy in sarcoma patients. Preclinical data has demonstrated comparable inhibitory effects of pazopanib against a number of targets including VEGFR-1, VEGFR-2, VEGFR-3, PDGFR- α , PDGFR- β , and c-Kit³. In a phase II study published in JCO in 2009, Sleijfer et al. demonstrated that pazopanib is well-tolerated in patients with relapsed or refractory advanced soft-tissue sarcoma⁴. Further, there is data from a phase III study of pazopanib in previously treated metastatic soft tissue sarcoma patients which demonstrated a progression free survival of 4.6 months for pazopanib vs. 1.6 months for placebo. Overall survival in the pazopanib group was 12.5 months⁵.

1.3 Rationale

Pazopanib is FDA approved as a second line and beyond treatment for metastatic soft tissue sarcoma. There is a population of elderly and debilitated soft tissue sarcoma patients that are not fit for standard first line chemotherapy that is doxorubicin based. As pazopanib is well tolerated with minimal side effects, we propose a phase II study to evaluate pazopanib as a first-line agent in patients with non-resectable or metastatic disease who are not candidates for cytotoxic chemotherapy.

1.4 Background of Correlative Studies

Sleijfer et al. recently published a translational study in which they evaluated whether cytokine levels in the patients enrolled in EORTC 62043, the phase II study of pazopanib in soft tissue sarcoma, correlated with PFS and OS. They measured levels of several cytokines at baseline and 12 weeks after beginning pazopanib therapy and demonstrated that baseline levels were not predictive, but that high sVEGFR2 and low PIGF were associated with a more favorable PFS at 12 weeks (OR 0.636, 95% CI 0.413-

0.977, P=0.039) and (OR 1.081, 95% CI 1.007-1.160, P=0.0318) respectively. There was also a trend toward high sVEGFR2 at week 12 and increased OS and a statistically significant association between low PIGF levels at week 12 and longer OS (HR 1.061, 95% CI 1.025-1.099, P=0.0009) ⁶.

We propose to measure sVEGFR2 and PIGF levels at baseline, 4 weeks, 8 weeks, and 12 weeks to both verify the results of Sleijfer et al and to determine if there is an even earlier correlation that can be detected between levels of these cytokines and PFS as well as OS which may allow us to better predict treatment response early on in therapy

In addition, plasma pazopanib concentrations will be determined immediately prior to the first dose of each dose escalation, then after steady-state is reached at 800 mg QD (after at least 10 days of 800 mg QD administration). These PKs will only be performed in the first 10-20 patients enrolled at Washington University.

2.0 OBJECTIVES

2.1 Primary Objective

To determine the clinical benefit rate (CR + PR + SD) in patients with soft tissue sarcoma not candidates for chemotherapy treated with first-line pazopanib at 16 weeks.

2.2 Secondary Objectives

1. To determine the rate of progression-free survival (PFS) in patients with soft tissue sarcoma not candidates for chemotherapy treated with first-line pazopanib.
2. To determine the rate of overall survival (OS) in patients with soft tissue sarcoma not candidates for chemotherapy treated with first-line pazopanib.
3. To evaluate the quality of life of patients with soft tissue sarcoma not candidates for chemotherapy treated with first-line pazopanib.
4. To correlate serum sVEGFR2 and PICG levels with outcomes.

3.0 PATIENT SELECTION

3.1 Inclusion Criteria

1. Histologically confirmed diagnosis of nonresectable or metastatic soft tissue sarcoma. The following histologies are excluded: embryonal rhabdomyosarcoma, chondrosarcoma, osteosarcoma, Ewing tumors, primitive neuroectodermal tumors, gastrointestinal stromal tumors, dermatofibrosarcoma protuberans, inflammatory myofibroblastic sarcoma, and mixed mesodermal tumors of the uterus.

2. Evaluable disease by imaging or physical exam OR measurable disease defined as at least one lesion that can be accurately measured in at least one dimension (longest diameter to be recorded) as ≥ 10 mm with CT scan, as ≥ 20 mm by chest x-ray, or ≥ 10 mm with calipers by clinical exam.
3. Not a candidate for chemotherapy as determined by the treating physician.
4. Age ≥ 18 years
5. ECOG performance status ≤ 2 (see Appendix A).
6. Normal bone marrow and organ function as defined below:
 - a. Absolute neutrophil count $\geq 1,500/\text{mcl}$
 - b. Platelets $\geq 100,000/\text{mcl}$
 - c. Hemoglobin ≥ 9.0 g/dL
 - d. PT or INR $\leq 1.2 \times$ IULN (if not receiving anticoagulation therapy)
 - e. PTT $\leq 1.2 \times$ IULN (if not receiving anticoagulation therapy)
 - f. Total bilirubin $\leq 1.5 \times$ IULN or $\leq 3.0 \times$ IULN with normal AST and ALT in patients with Gilbert's disease
 - g. AST(SGOT)/ALT(SGPT) $\leq 2.5 \times$ IULN
 - h. Creatinine ≤ 1.5 mg/dL OR creatinine clearance ≥ 30 mL/min/1.73 m² for patients with creatinine levels above 1.5 mg/dL
 - i. UPC < 1 (in like units) or, if UPC ≥ 1 , 24-hour urine protein < 1 g; use of urine dipstick for renal function assessment is not acceptable.

Notes:

Subjects may not have had a transfusion within 7 days of screening assessments. Concomitant elevation of bilirubin and AST/ALT above the IULN is not allowed.

Patients receiving anticoagulation therapy are eligible if their INR is stable and within the recommended range for the desired level of anticoagulation.

7. Ability to swallow and retain oral tablets.
8. Women of childbearing potential must agree to use adequate contraception (hormonal or barrier method of birth control, abstinence) prior to study entry and for the duration of study participation. Should a woman become pregnant or suspect she is pregnant while participating in this study, she must inform her treating physician immediately.
9. Ability to understand and willingness to sign an IRB approved written informed consent document.

3.2 Exclusion Criteria

1. Eligible for cytotoxic chemotherapy.
2. Prior systemic therapy for this type of sarcoma. Neoadjuvant or adjuvant therapy more than two years prior would not apply.
3. Prior treatment with any VEGFR tyrosine kinase inhibitor.
4. Administration of any non-oncologic investigational drug within 30 days or 5 half-lives (whichever is longer) prior to the first dose of pazopanib.
5. Use of a strong CYP3A4 inhibitor less than 14 days prior to initiation of study treatment (please refer to Section 5.2.5 and Appendix F).
6. A history of other malignancy ≤ 5 years previous with the exception of basal cell or squamous cell carcinoma of the skin which were treated with local resection only or carcinoma *in situ* of the cervix.
7. Known brain metastases.
8. A history of allergic reactions attributed to compounds of similar chemical or biologic composition to pazopanib or other agents used in the study.
9. Any ongoing toxicity from prior anti-cancer therapy that is $>$ grade 1 and/or that is progressing in severity (except alopecia).
10. Uncontrolled intercurrent illness including, but not limited to, ongoing or active infection, uncontrolled seizure disorder, or psychiatric illness/social situations that would limit compliance with study requirements.
11. Corrected QT interval (QTc) $>$ 480 msec.
12. History of any one or more of the following cardiovascular conditions within the past 6 months: cardiac angioplasty or stenting, myocardial infarction, unstable angina pectoris, coronary artery bypass graft surgery, symptomatic peripheral vascular disease, class III or IV congestive heart failure as defined by the New York Heart Association (see Appendix B).
13. Poorly controlled hypertension (defined as systolic blood pressure of ≥ 140 mmHg or diastolic blood pressure of ≥ 90 mmHg). Note: initiation or adjustment of antihypertensive medication(s) is permitted prior to study entry. Following antihypertensive medication initiation or adjustment, blood pressure must be reassessed three times at approximately 2-minute intervals. At least 24 hours must have elapsed between antihypertensive medication initiation or adjustment and blood pressure measurement. These three values should be averaged to obtain the mean diastolic and systolic blood pressures, which must be $<$ 140/90 mmHg in order for a patient to be eligible for the study.

14. Clinically significant gastrointestinal abnormalities that may increase the risk for gastrointestinal bleeding, including (but not limited to) active peptic ulcer disease, known intraluminal metastatic lesions with risk of bleeding, inflammatory bowel disease (e.g., ulcerative colitis, Crohn's disease) or other GI conditions with increased risk of perforation, history of abdominal fistula or intra-abdominal abscess within 28 days prior to beginning study treatment.
15. Clinically significant gastrointestinal abnormalities that may affect absorption of pazopanib, including (but not limited to) malabsorption syndrome or major resection of the stomach or small bowel.
16. History of cerebrovascular accident including transient ischemic attack, pulmonary embolism (PE) (including asymptomatic or previously treated PE), or untreated deep venous thrombosis within the past 6 months. Patients with DVT who are being treated with therapeutic anti-coagulating agents are eligible.
17. Major surgery or trauma within 28 days prior to first dose of pazopanib and/or presence of any non-healing wound, fracture, or ulcer (procedures such as catheter placement not considered to be major surgery).
18. Evidence of active bleeding or bleeding diathesis.
19. Known endobronchial lesions and/or lesions infiltrating major pulmonary vessels that increase the risk of pulmonary hemorrhage. Note: lesions infiltrating major pulmonary vessels (contiguous tumor and vessels) are excluded; however, the presence of a tumor that is touching but not infiltrating (abutting) the vessels is acceptable (CT with contrast is strongly recommended to evaluate such lesions). Large protruding endobronchial lesions in the main or lobar bronchi are excluded; however, endobronchial lesions in the segmented bronchi are allowed. Lesions extensively infiltrating the main or lobar bronchi are excluded; however, minor infiltrations in the wall of the bronchi are allowed.
20. Recent hemoptysis ($\geq \frac{1}{2}$ teaspoon of red blood within 8 weeks before first dose of pazopanib).
21. Pregnant and/or breastfeeding. Patient must have a negative serum pregnancy test within 14 days of study entry.
22. Known HIV-positivity. Appropriate studies will be undertaken in patients receiving combination antiretroviral therapy when indicated.

3.3 Inclusion of Women and Minorities

Both men and women and members of all races and ethnic groups are eligible for this trial.

4.0 REGISTRATION PROCEDURES

Patients must not start any protocol intervention prior to registration through the Siteman Cancer Center.

The following steps must be taken before registering patients to this study:

1. Confirmation of patient eligibility by Washington University
2. Registration of patient in the Siteman Cancer Center database
3. Assignment of unique patient number (UPN)

Once the patient has been entered in the Siteman Cancer Center database, the WUSM coordinator will forward verification of enrollment and the UPN via email.

4.1 Confirmation of Patient Eligibility

Confirm patient eligibility by collecting the information listed below and scanning and emailing it to the research coordinator listed in the *Siteman Cancer Center Clinical Trials Core Protocol Procedures for Secondary Sites* packet at least one business day prior to registering patient:

1. Your name and contact information (telephone number, fax number, and email address)
2. Your site PI's name, the registering MD's name, and your institution name
3. Patient's race, sex, and DOB
4. Three letters (or two letters and a dash) for the patient's initials
5. Currently approved protocol version date
6. Copy of signed consent form (patient name may be blacked out)
7. Planned date of enrollment
8. Completed eligibility checklist, signed and dated by a member of the study team
9. Copy of appropriate source documentation confirming patient eligibility

4.2 Patient Registration in the Siteman Cancer Center Database

Registrations may be submitted Monday through Friday between 8am and 5pm CT. Urgent late afternoon or early morning enrollments should be planned in advance and coordinated with the Washington University research coordinator. Registration will be confirmed by the research coordinator or his/her delegate by email within one business day. Verification of eligibility and registration should be kept in the patient chart.

All patients at all sites must be registered through the Siteman Cancer Center database at Washington University.

4.3 Assignment of UPN

Each patient will be identified with a unique patient number (UPN) for this study. Patients will also be identified by first, middle, and last initials. If the patient has no middle initial, a dash will be used on the case report forms (CRFs). All data will be recorded with this identification number on the appropriate CRFs.

5.0 TREATMENT PLAN

5.1 Agent Administration

Pazopanib will be started at a dose of 200 mg BID for four days, then escalated to a dose of 400 mg BID for four days (if tolerated), then escalated once more to a dose of 800 mg QD for the duration of participation (if tolerated) or until dose reduction, if necessary. Pazopanib should be taken orally without food at least one hour before or two hours after a meal. One cycle of pazopanib is 28 days. The tablets should be swallowed whole and must not be crushed or broken. The time of day the tablets are taken should be relatively constant.

If a dose is missed, the subject should take the dose as soon as possible, but only if there are 12 or more hours remaining before the next dose is due. If the next dose is due in less than 12 hours, the subject should skip the missed dose and take the next dose as scheduled.

If vomiting occurs after taking pazopanib, the subject should not take a replacement dose for that dose, but should resume taking pazopanib at the next scheduled dose. If vomiting persists, the subject should be instructed to notify the investigator.

Please note that a Monday or Thursday start is recommended to avoid weekend blood draws for pharmacokinetic testing.

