9.3 Pharmacokinetics

Twenty mL of blood will be drawn at the following time points to measure plasma pazopanib concentrations:

- Baseline (prior to initiation of treatment)
- Cycle 1 Day 5 (prior to escalation to 400 mg BID)
- Cycle 1 Day 9 (prior to escalation to 800 mg QD)
- Cycle 2 Day 1

Blood should be collected in 2 EDTA purple top tubes and 1 red top tube. DNA (for future use), serum, and whole cells should be prepared and frozen down prior to shipment using standard laboratory techniques. Samples should be labeled with the corresponding patient's study ID number, initials, and date of collection.

These PKs will only be performed in the first 11 patients enrolled at Washington University. This testing was completed as of amendment 4.

SHIP FROZEN IN BATCHES TO:

[name] [name] – Research lab
[name]
[name]
[name]

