10.0 STUDY CALENDAR

Screening assessments must be performed no more than 14 days prior to start of study treatment, except scans which may take place up to 28 days prior to the start of treatment. After the start of study treatment, there is a ± 7 day window for all exams, scans, labs and procedures to be performed. Please note, there is also a ± 7 day window for treatment and for routine office visits.

	Screening	D1 of each cycle	C1D5	C1D8	C1D9	C1D15 and C2D15	End of every even-numbered cycle	EOT	F/U ¹	
Informed consent	X									
PE, H&P, PS	X	X						X		
VS	X	X		X				X		
CBC	X	X		X				X		
CMP	X	X		X				X		
LFTs ²	X	X ²		X ²		X ²		X		
Pregnancy test ³	X							X		
UPC	X	X ⁴						X		
TSH, FT4	X	X ⁵								
PT/PTT, INR	X							X		
ECG	X	X ⁶								
ECHO ¹⁰	X									
CT scan	X						X	X		
Pazopanib		X	-----					X ⁷		
FACT-G		X ⁸				X ⁸				
Blood for biomarkers		X ⁹								
Collect/review drug diary		X								
Toxicity assessment	X	X						X		

1. Every 3 months until death.

2. Monitor serum liver tests (total bilirubin, ALT/AST) before initiation of treatment with pazopanib and on C1D15, C2D1, C2D15, C3D1, C4D1, C5D1, and as clinically indicated (± 3 days). Periodic monitoring should continue after C5.

3. Women of childbearing potential only.

4. D1 of each cycle through C6, then D1 of every even-numbered cycle thereafter.

5. Monitor between every 8 to every 16 weeks.

6. C2D1, C4D1, C7D1, and then every 16 weeks (D1 of every 4th cycle) until EOT.

7. To be taken PO each day. Each cycle is 4 weeks long. See Section 5.1 for dosing instructions.

8. Baseline (prior to C1D1), C1D15, and D1 of every cycle thereafter.

9. Baseline (prior to C1D1), C2D1, C3D1, and C4D1.

10. Baseline (prior to C1D1) and periodic reassessment as needed and/or as indicated. Consistent diagnostic imaging should be used throughout study.

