11.0 DATA SUBMISSION SCHEDULE

Case report forms with appropriate source documentation will be completed according to the schedule listed in this section.

Case Report Form	Submission Schedule
Original Consent Form	Prior to registration
Registration Form Eligibility Form On-Study Form	Prior to starting treatment
Treatment Form Pill Diary	Every cycle
QOL Form	Baseline C1D15 Day 1 of every cycle thereafter
Correlatives Form	Baseline C1D5 C1D9 C2D1 C3D1 C4D1
Toxicity Form	Continuous
Treatment Summary Form	Completion of treatment
Follow Up Form	Every 3 months until death
Tumor Measurement Form	Baseline, end of every even numbered cycle, and end of treatment
MedWatch Form	See Section 7.0 for reporting requirements

Any queries generated by Washington University must be responded to within 28 days of receipt by the participating site. The Washington University research team will conduct a regular review of data status at all secondary sites, with appropriate corrective action to be requested as needed.

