APPENDIX B: New York Heart Association (NYHA) Functional Classification

NYHA Class	Symptoms
I	No symptoms and no limitation in ordinary physical activity, e.g., shortness of breath when walking, climbing stairs, etc.
II	Mild symptoms (mild shortness of breath and/or angina) and slight limitation during ordinary activity.
III	Marked limitation in activity due to symptoms, even during less-than-ordinary activity, e.g., walking short distances (20-100 m). Comfortable only at rest.
IV	Severe limitations. Experiences symptoms even while at rest. Mostly bedbound patients.

The Criteria Committee of the NYHA, Nomenclature and Criteria for Diagnosis of Diseases of the Heart and Great Vessels. 9th ed. Boston, Mass: Little, Brown & Co; 1994:253-256.

APPENDIX C: Medication Diary – Cycle 1

Today's Date: _____

Cycle 1

Agent: Pazopanib

Patient Name: _____

Study ID# 201501057

1. Take pazopanib by mouth under fasting conditions (at least one hour before or two hours after a meal).
2. Take pazopanib with a glass of water and drink the glass of water in as little time as possible.
3. Record the date, time and amount of drug taken. Write "1-200mg", "2-200mg", "3-200mg", or "4-200mg."
4. If you forgot to take your dose, do not take that dose. Restart pazopanib at the next scheduled dose.
5. If you vomit or notice any side effects, list in the comments section. Do not re-take a dose after vomiting.
6. Return this form and used pill bottles to your study coordinator when you go to your next appointment.

Important Dosing Instructions: Slowly increase the dose when you first start taking pazopanib.

First 4 days (Cycle 1, Days 1-4): Take **one 200-mg pill** in the morning, and **one 200-mg pill** in the evening.

Next 4 days (cycle 1, Days 5-8): Take **two 200-mg pills** in the morning, and **two 200-mg pills** in the evening.

Cycle 1, Day 9 and beyond: Take **four 200-mg pills** in the morning. *Do not take drug in the evening.*

Dose changes: If you experience side effects, you may be asked to discontinue or reduce the dose.

Day	Date	Morning		Evening		Comments
		Pill # and mg	Time Taken	Pill # and mg	Time Taken	
1						
2						
3						
4						
5						
6						
7						
8						
9						
10						
11						
12						
13						
14						
15						
16						
17						
18						
19						
20						
21						
22						

23					
24					
25					
26					
27					
28					

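### The Cycle 1 diary (Appendix C) leaves out Section 5.1's tolerance condition at the Day 5 dose step, so unless staff learn of a problem, a patient following it doubles the daily dose without that condition being applied

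*Combined protocol and SAP*

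**What the plan says.** Section 5.1 (Agent Administration) sets out a stepped start: 200 mg BID for four days, "then escalated to a dose of 400 mg BID for four days (if tolerated"), then 800 mg QD, again subject to tolerance. The section does not define tolerance. It adds one reporting instruction for early symptoms: "If vomiting persists, the subject should be instructed to notify the investigator".

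Appendix C (Medication Diary, Cycle 1) gives patients the same doses on the same days. Its second step opens "Next 4 days (cycle 1, Days 5-8") and goes straight on to two 200 mg tablets morning and evening. Neither that line nor the Day 9 line carries a tolerance condition. On side effects the diary has two statements: "If you vomit or notice any side effects, list in the comments section", and, below the dose steps, "If you experience side effects, you may be asked to discontinue or reduce the dose".

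In Section 10.0 (Study Calendar), as far as the table survives extraction, the row "Toxicity assessment" is marked at screening, Day 1 of each cycle and end of treatment. Diary collection and review is marked at Day 1 of each cycle. The C1D5 column appears empty, and C1D8 carries vital signs and blood tests. A pharmacokinetic draw was once made on C1D5, before the step, in the first 11 patients at the coordinating site. Section 9.3 says of it: "This testing was completed as of amendment 4".

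**The concern.** The protocol makes the Day 5 increase depend on how the patient has done at the lower dose. The patient's own instructions do not. Someone has to apply the condition, and on paper it is neither the patient, who is told to increase, nor a scheduled contact, since none is marked before the step. It falls to staff, who can act only if they hear of a problem in time, and the diary directs side effects to a comments box.

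What is at stake is patient safety in the first week. Section 1.3 describes the target population as older or frail patients unfit for doxorubicin-based treatment. Section 6.0 requires interruption for some events, for example hemoptysis even at Grade 1, symptomatic hypertension, and other clinically significant drug-related events of Grade 2 or 3. A patient with one of these on Day 4 who has not told the site would be following written instructions by doubling the dose on Day 5.

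**Working it through.** **1. Reproduce the dose steps.** Inputs are the doses in Section 5.1 and the tablet counts in Appendix C.

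| Days | Section 5.1 | Appendix C | mg/day | Condition in 5.1 | Condition in diary line |
|---|---|---|---|---|---|
| 1-4 | 2 × 200 mg | 2 tablets × 200 mg | 400 | none | none |
| 5-8 | 2 × 400 mg | 4 tablets × 200 mg | 800 | tolerance | none |
| 9 on | 1 × 800 mg | 4 tablets × 200 mg | 800 | tolerance | none |

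The doses agree throughout. The only difference is the condition.

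**2. Find the step that matters.** Day 5: 800 / 400 = 2.0. Day 9: 800 / 800 = 1.0. Day 5 is the only step that raises the daily total, from 400/800 = 50% to 800/800 = 100% of the target.

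**3. Exposure before the next marked assessment.** From the Day 5 step to a visit on nominal Day 8, the patient takes 3 days × 2 = 6 doses, or 7 if the Day 8 morning dose comes before the visit.

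- Following the diary: 6 × 400 = 2,400 mg to 7 × 400 = 2,800 mg.
- Held at 200 mg BID: 6 × 200 = 1,200 mg to 7 × 200 = 1,400 mg.
- Difference: 1,200 to 1,400 mg.

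These use nominal days. The calendar's ±7-day window can move the C1D8 visit either way.

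**4. Does anything prompt a report before Day 5?**

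- *Diary dose-change line:* the patient may be asked to stop or reduce. It is passive and works only once staff know.
- *Diary comments box:* records the event but does not tell the patient to call or to hold.
- *Section 5.1 on persistent vomiting, and Section 5.2.2 on symptoms of hypoglycemia:* these are prompts to report, limited to those symptoms.
- *Section 11.0:* the "Toxicity Form" is continuous, but it captures what the site already knows.
- *Section 13.0:* the principal investigator and the research patient coordinator watch for serious toxicity throughout. This too depends on word reaching the site.
- *Return of the diary at the next appointment:* this may bring the form in at C1D8, which nominally falls after the step.
- *Section 6.0:* governs the dose once an event is known.

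Apart from vomiting and hypoglycemia, nothing in the visible text prompts the patient to report a side effect before stepping up.

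**The case against.** The strongest reply is that the diary is an intake log and does not override the protocol. The investigator remains bound by Sections 5.1 and 6.0, the diary itself warns that side effects may lead to a dose change, and staff watch for serious toxicity throughout. Consent pages, where an instruction to call the study doctor often sits, were removed from the text under review, and the calendar is read from a damaged table. All of this stands as a limit on the size of the problem. It does not supply the missing condition: each safeguard acts after the site hears of a problem, and the diary does not ask the patient to make contact.

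A reader might infer more than the documents support, in three ways.

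- *That every patient who follows the diary doubles the dose regardless of tolerance.* The dose-change line means the step goes ahead unless staff intervene, which is a narrower statement.
- *That a number of affected patients can be given by applying an assumed early side-effect rate to the 56 planned patients.* The documents give no rate of side effects by Day 4. The first 11 patients at the coordinating site had a draw scheduled before the step. Nor is a side effect the same as intolerance: for drug-related events in its residual category, Section 6.0 continues dosing at Grade 1.
- *That this is an overdose or threatens the primary endpoint.* The dose is the planned one on the planned day, and nothing here bears on the 16-week clinical benefit rate, its significance level or its power.

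**Conclusion.** The concern holds as a mismatch between the dosing rule and the patient's instructions. Section 5.1 permits the Day 5 doubling only if the lower dose is tolerated; Appendix C instructs it without that condition. The size that can be stated is per patient: 400 to 800 mg a day, and nominally 1,200 to 1,400 mg more drug by C1D8 than if held at the lower dose.

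The conclusion assumes that the patient follows the diary as written, that no instruction outside the visible text tells the patient to call first, and that the C1D5 calendar column is as empty as it appears. It should be corrected, because it concerns safety and the remedy is small. Confidence is medium, given the partial safeguards and the text that cannot be seen.

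**What to change.** Add to the Day 5 line of Appendix C: *Increase only if you are tolerating the current dose. If you have bothersome or new significant side effects, or are unsure, stay at the current dose and call the study team before increasing.* Put the same tolerance wording on the Day 9 line. The daily total does not rise there, but Section 5.1 sets the same condition.

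The wording should follow tolerance rather than the mere presence of side effects. A line telling patients not to increase with any side effect would be stricter than Section 5.1 and could hold back doses for trivial symptoms. Once called, the study team applies Section 6.0, including interruption where it is required; staying at the current dose is only the interim instruction.

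The cost is a diary reprint, a few extra calls, and a short delay in escalation for some patients. No new visit is needed. Sites should not assume the call will fall on a weekday: the Monday or Thursday start in Section 5.1 is only recommended, and its stated purpose was to avoid weekend pharmacokinetic draws, which are now complete.
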